#### 3.2 Overall Study Motivation, Aim and Hypothesis

Many emergency department (ED) patients with sepsis do not receive antibiotics and other care within intervals recommended in international guidelines. Efforts to accelerate treatment, however, may lead to overtreatment and other adverse effects. The goal of this project is to determine the potential effectiveness and tradeoffs of a Code Sepsis program for ED sepsis patients.

Aim: Establish the feasibility and effects of a team-based Code Sepsis protocol designed to accelerate antibiotic initiation for ED patients with suspected sepsis.

Using preexisting infrastructure, implement prehospital- or triage-activated Code Sepsis ED teams in a single ED and compare sepsis patients' door-to-antibiotic times pre- and post-implementation, controlling for unrelated temporal trends with observational data from two non-intervention EDs.

Hypothesis: Prehospital or triage-based activation of an ED team prepared to rapidly diagnose and treat sepsis decreases door-to-antibiotic time without increasing overtreatment.

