#### 3.7.2 Secondary outcomes

- Clinical/patient-centered secondary outcomes (measured among all ED sepsis patients):
  - 1) All-cause mortality to day 30
  - 2) All-cause mortality to 1 year
  - 3) In-hospital all-cause mortality
  - 4) Hospital charges: Amount charged to patient for their medical care during index ED visit and associated hospitalization.
  - 5) Hospital length of stay
- Process/feasibility secondary outcomes
  - 1) Code Sepsis activation rate: Measured as the percentage of all ED patients for whom the Code Sepsis protocol was activated.
  - 2) Code Sepsis activation accuracy metrics. Accurate Code Sepsis activation is defined as activation for patients who have sepsis while in the ED and no activation for patients who do not have sepsis in the ED.
- Adverse effects and unintended outcomes of protocol implementation

- 1) Antibiotic utilization percentage: measured as the fraction of (1) all ED patients; (2) Code Sepsis activation patients; or (3) "likely" sepsis patients who received IV or IV-equivalent antibiotics.
- 2) Antibiotic spectrum: Total Stenehjem antibiotic spectrum score for all antibiotics administered in first 24 hours, measured for (1) all ED patients or (2) sepsis patients
- 3) Antibiotic overtreatment rate: Percentage of "sepsis mimic" patients who received IV or IVequivalent antibiotics in the ED.
- 4) New onset C. difficile colitis incidence: Percentage of (1) all ED patients and (2) ED sepsis patients with a positive stool test for *Clostridium difficile* colitis between 72 hours and 90 days after ED arrival.
- 5) Adverse drug & allergic reaction incidence: Measured as the fraction of 1) all ED patients and (2) ED sepsis patients with a discharge diagnosis code consistent with anaphylaxis or with an adverse reaction to antibiotics (see Appendix C).
- Potential exploratory outcomes
  - 1) Measures of organ failure trajectory, to include change in the SOFA score between hospital day 1 and hospital day 3, and overall and organ-specific measures of organ failure-free days through day 28.

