#### 8.1.3. Risks to patients exposed to the Code Sepsis protocol

Patients presenting to the intervention hospital during phases #2 and 3 (run-in implementation and full implementation) will be exposed to and may receive care using the "Code Sepsis" version of standard care. The Code Sepsis protocol is designed to accelerate evaluation, testing, and treatments that the patient would have eventually received under now current standard care. The Code Sepsis intervention is therefore expected to pose no more than minimal risks to ED patients exposed to the protocol, including specifically sepsis patients for whom the Code Sepsis protocol is activated. The potential risks to subjects due to this protocol include:

- 1) Adverse drug reactions or antibiotic-associated infections related to unnecessary or overtreatment antibiotic treatment with prespecified regimens.
- 2) Delay in diagnosis of non-infectious problems due to focus on sepsis or infection related to Code Sepsis activation.
- 3) Delay in care related to resource allocation away from non-Code Sepsis patients without sepsis (bystanders without sepsis).
- 4) For sepsis patients for whom the Code Sepsis protocol is not activated (i.e. bystanders with sepsis), delay in care related to lower index of suspicion for sepsis leading to delayed diagnosis or resource allocation away from these patients.

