cohort	(3) Primary ICD-10-CM discharge diagnosis code of venous thromboembolism or congestive heart failure and no ICD- 10-CM discharge diagnosis code for infection in any position	
 
within 6 hours prior to study ED arrival
 
(3) Subsequent eligible ED visit after first eligible encounter during an analysis window
 
(4) Left ED without evaluation or treatment
 
	

\* For analyses including all eligible encounters for a given cohort (i.e., ignoring exclusion criteria #3), the name of the indicator variable is appended with "\_sens" (e.g. "cohort\_sepsis\_sens")

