### Safety outcomes

	Analysis		
Outcome	cohort	Description	Outcome variable
Antibiotic utilization	All patient	Receipt of IV or equivalent antibiotics within 24	abx_24h
	cohort	hours of ED arrival	
Antibiotic utilization	Sepsis	Receipt of of receiving IV or equivalent antibiotics	abx_24h
	high-risk	within 24 hours of ED arrival	
	cohort		
Potential adverse effect	Sepsis	Antibiotic-related adverse event (a discharge	<pre>icd10_ae_summary</pre>
of antibiotics	cohort	diagnosis code consistent with anaphylaxis or	
		with an adverse reaction to antibiotics)	
Potential adverse effect	All patient	Antibiotic-related adverse event (a discharge	<pre>icd10_ae_summary</pre>
of antibiotics	cohort	diagnosis code consistent with anaphylaxis or	
		with an adverse reaction to antibiotics)	
New-onset C difficile	Sepsis	New positive stool test for Clostridium difficile	cdiff_72h_new_analysis
	cohort*	colitis between 72 hours and 90 days after ED	ineligible)
		arrival	
		* Excludes patients with a positive C. difficile	
		assay in the 14 days preceding ED arrival or	
		within 72 hours following ED arrival	

	Analysis		
Outcome	cohort	Description	Outcome variable
New-onset C difficile	All patient cohort*	New positive stool test for Clostridium difficile colitis between 72 hours and 90 days after ED arrival	cdiff_72h_new_analysis (missing if ineligible)
		* Excludes patients with a positive C. difficile assay in the 14 days preceding ED arrival or within 72 hours following ED arrival	
Antibiotic	Sepsis	Receipt of antibiotics in the ED among ED	abx_ed
overtreatment rate	mimic	patients with a primary hospital discharge	
	cohort	diagnosis of congestive heart failure or venous	
		thromboembolism	
False-positive	Sepsis	Final adjudicated infection status is "not	uninfected
presumptive infection	cohort	infected" among ED patients meeting sepsis	
diagnosis rate		criteria	

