### Data analysis

Analyses for causal inference regarding primary, secondary and safety outcomes will employ a quasi-experimental method called *difference-in-difference* (DID) analysis to control for secular trends and confounding of unknown individual factors associated with the outcome of interest. The DID approach will provide an estimate of the effect of the Code Sepsis intervention on primary, secondary, and safety outcomes by comparing the intervention and control hospitals during the pre- and post-implementation periods (Figure 1).

For the primary outcome, DID analysis will use multivariable linear regression to compare the adjusted mean door-to-

antibiotic time (primary outcome) at the intervention hospital

pre- versus post-implementation of the Code Sepsis protocol using the measured change at contemporaneous control non-intervention hospitals to control for pre-/post-intervention changes not attributable to protocol implementation after adjustment for potential confounders.

The following equation will be used to estimate the adjusted mean differential change in the primary outcome, door to antibiotic time:

$$Y_{igt} = \beta_0 + \beta_1 Int_g + \beta_2 Post_t + \beta_3 (Int_g * Post_t) + \beta_4 Cov$$

Where  $Y_{igt}$  is the door-to-antibiotic time for patient *i* treated at an intervention or non-intervention ED *g* at pre- or post-intervention time *t*. *Int* is a binary indicator for the subject being treated at an intervention hospital; *Post* is a binary indicator the post-intervention period; and *Cov* represents a vector of patient-level covariates. The  $\beta_3$  parameter from the regression model presented above estimates the adjusted mean differential change in door-to-antibiotic time observed in the Code Sepsis intervention hospital compared to the control hospital. We will consider the Code Sepsis intervention to have had an impact if  $\beta_3$  is statistically significant and different from zero.

The parallel trend assumption will be tested using the approach outlined by Callaway and Sant'Anna. This approach allows for testing the parallel trend assumption after conditioning on covariates. This approach is

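### The overtreatment rate in sepsis mimics counts only antibiotics given in the ED, so it can rise through earlier dosing or longer ED stays without extra patients being treated; a paired 24-hour outcome would separate the two.

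*SAP*

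**What the plan says.** The overtreatment outcome is defined the same way in both documents. The SAP (Safety outcomes) uses "Receipt of antibiotics in the ED among ED" patients in the mimic cohort, variable `abx_ed`. Protocol section 3.7.2 counts mimic "patients who received IV or IVequivalent antibiotics in the ED".

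The denominator comes from discharge coding (SAP, Inclusion/exclusion criteria): a primary code for heart failure or venous thromboembolism and no "discharge diagnosis code for infection in any position". Patients given antibiotics in the 6 hours before arrival are excluded. Nothing in the definition depends on where or when an antibiotic was given after arrival.

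The neighbouring utilization outcomes use a different window: "Receipt of IV or equivalent antibiotics within 24" hours of ED arrival, variable `abx_24h`. They are planned in the all-patient and sepsis high-risk cohorts, not in the mimic cohort.

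The protocol hypothesis (section 3.2) is that early team activation "decreases door-to-antibiotic time without increasing overtreatment". Section 8.1.3 describes the intervention as "designed to accelerate evaluation, testing, and treatments that the patient would have eventually received under now current standard care". The SAP (Data analysis) applies DID to the safety outcomes as well: "Analyses for causal inference regarding primary, secondary and safety outcomes will employ a quasi-experimental method". The control EDs stay on standard care throughout.

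**The concern.** Code Sepsis is meant to bring treatment forward, and this outcome stops counting when the patient leaves the ED. Take a heart-failure patient who would have received an unneeded antibiotic on the ward. That patient counts as not overtreated before implementation, but as overtreated afterwards if the same dose is given in the ED. Because the denominator is fixed by discharge codes, any such shift goes straight into the numerator. Because the control EDs do not adopt the protocol, the DID does not remove it.

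The mimic rate is the planned outcome that bears most directly on the no-more-overtreatment half of the hypothesis. The protocol (section 3.5, and Phase 4 in section 5) expects continuation or wider adoption of Code Sepsis to depend on the results. A timing shift read as added treatment, or a shorter ED stay that hides added treatment, could therefore affect a practical decision.

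**Working it through.** Neither document gives a rate, sample size or power for this outcome, so there is no planned figure to reproduce. The check is an identity.

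**Inputs.** T is the share of mimics given an antibiotic within 24 hours of arrival. f is the share of those treated patients who receive it in the ED. Neither is in the documents, and all values below are assumptions. Doses given in the ED are taken to fall within 24 hours of arrival.

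**Formulas.** The ED rate is T × f and the 24-hour rate is T. With subscripts 0 and 1 for the two periods at the intervention site, and no change at the control EDs:

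- DID on `abx_ed` = T1 × f1 − T0 × f0
- DID on `abx_24h` = T1 − T0

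If no extra patient is treated (T1 = T0 = T), the first becomes T × (f1 − f0) and the second is 0.

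**Illustration with T unchanged**

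| T | f0 to f1 | `abx_ed` before | `abx_ed` after | DID on `abx_ed` | Rate ratio | DID on `abx_24h` |
|---|---|---|---|---|---|---|
| 10% | 0.90 to 0.95 | 9.0% | 9.5% | +0.5 points | 1.06 | 0 |
| 20% | 0.80 to 0.90 | 16.0% | 18.0% | +2.0 points | 1.125 | 0 |
| 30% | 0.60 to 0.80 | 18.0% | 24.0% | +6.0 points | 1.33 | 0 |

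**How plausible is the upper end?** The shift cannot exceed 1 − f0. Moving f from 0.60 to 0.80 means that 0.20/0.40 = 50% of mimics otherwise treated on the ward get their dose in the ED instead. The only activation figure in the plan is 30% of sepsis patients (protocol section 7.3, called conservative there). Suppose 30% also applied to ward-treated mimics, every such dose moved, and there was no spillover to other patients. Then, at T = 20%:

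- f0 = 0.60: shift 0.30 × 0.40 = 0.12, so DID = 0.20 × 0.12 = +2.4 points
- f0 = 0.90: shift 0.30 × 0.10 = 0.03, so DID = 0.20 × 0.03 = +0.6 points

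**The other direction.** A shorter ED stay at the intervention site lowers f. With T = 20% and f falling from 0.90 to 0.80, `abx_ed` falls from 18.0% to 16.0%, a DID of −2.0 points with no change in treatment. Equally, a true rise in T from 20% to 22.5% would be hidden completely, since 0.225 × 0.80 = 0.18 = 0.20 × 0.90. The SAP's safety covariates include no measure of ED stay.

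**Is the gap covered elsewhere?**

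- `abx_24h` in the all-patient and high-risk cohorts does not depend on treatment location, but those cohorts include infected patients. They cannot show whether mimics were treated more often.
- The false-positive infection diagnosis rate is measured in the sepsis cohort, where entry already requires an ED antibiotic.
- The predictive value of activation for infection is measured only at the intervention site after implementation, so it has no comparison.
- No listed sensitivity analysis changes the window of the mimic outcome.

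**The case against.** An ED-only window is a reasonable measure of ED prescribing. Code Sepsis is an ED protocol, the worry in protocol section 3.1 is anchoring and overtreatment of patients without sepsis, and an antibiotic given to a mimic in the ED is a direct record of that decision. A 24-hour window adds inpatient decisions. The window is the same in protocol and SAP, so the documents do not contradict each other. The SAP treats safety analyses as hypothesis generating, and no margin or decision rule is tied to `abx_ed`. A pure ward-to-ED shift also errs towards caution, because it suggests harm rather than hiding it. All of this stands, and it argues against replacing `abx_ed`. The last point does not cover a change in ED stay, which can also conceal added treatment.

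A reader might infer two stronger claims that the documents do not support.

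The first is that success on the primary outcome must produce an apparent harm here. The primary outcome is measured in sepsis patients who already received an antibiotic in the ED, with a planning mean of 170 minutes. It can improve with every dose staying inside the ED and with no shift among mimics, who are a separately defined cohort. The statement in section 8.1.3 that care is accelerated is a rationale about risk, not evidence that mimics would otherwise have been treated on the ward.

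The second is that the trial cannot tell faster treatment from overtreatment. The 24-hour utilization outcomes in two cohorts and the 24-hour spectrum scores in three give some information. What is missing is the direct check in the mimic cohort.

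**Conclusion.** The point holds as a conditional weakness of measurement. `abx_ed` mixes whether a mimic is treated with when, and with how long the ED stay lasts. If first doses move from ward to ED, its DID overstates added treatment by T × (f1 − f0). If ED stay changes at one site, the bias can go either way.

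The size cannot be derived from the documents. The range of 0.5 to 6 points rests wholly on assumed T (10-30%) and an assumed shift in f (5-20 points). The top of the range needs half of ward-treated mimics to move. If nearly all treated mimics already receive their first dose in the ED, the bias is small.

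The primary outcome is unaffected. This is an inexpensive improvement to one safety outcome, not a flaw that undermines the trial.

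**What to change.** Keep `abx_ed` as the prespecified mimic outcome, which leaves the SAP in line with protocol section 3.7.2. Add a paired row to the SAP's Safety outcomes table: `abx_24h` in the sepsis mimic cohort, analysed with the same DID and covariates and reported beside `abx_ed`.

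State the reading in advance. A rise in both is read as more treatment. A rise in `abx_ed` alone is read as earlier treatment or a longer ED stay. Base this on the two estimates and their confidence intervals, since a non-significant 24-hour result would not by itself show that treatment was unchanged. Record the addition in the SAP's version table.

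The cost is low. The variable is already defined, and no new data are needed. The downsides are one more hypothesis-generating safety analysis, and a 24-hour measure that includes some inpatient-initiated or prophylactic doses and so is less specific to ED decisions. Reporting the two together lets the reader see both.

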# Inclusion/exclusion criteria

Cohort	Inclusion	Exclusion	Cohort eligibility indicator variable*
ED sepsis cohort (primary analysis cohort)	
 
(1) Age ≥18 years
 
(2) Arrival to an intervention or control ED during study period
 
(3) Met all Sepsis-3 criteria in the ED
 
Acute organ failure in the ED defined by SOFA score while in the ED ,≥2 points above baseline
 
Suspected or confirmed infection while in the ED, based on having both: 
 
i. Administration of ,≥1 IV or IV-equivalent antibiotics while in the ED for suspected infection (i.e. antibiotics not given for prophylaxis)
 
ii. Collection of ,≥1 body fluid cultures while in the ED
 
 
 
	
 
Trauma patient
 
Subsequent eligible ED visit with sepsis after first eligible encounter during an analysis window
 
	cohort_sepsis
All adult ED patients cohort	
 
(1) Age ≥18 years
 
(2) Arrival to an intervention or control ED during study period
 
	
 
Trauma patient
 
Received antibiotics within 6 hours prior to study ED arrival
 
Subsequent eligible ED visit after first eligible encounter during an analysis window
 
Left ED without evaluation or treatment
 
	cohort_all
Sepsis high-risk cohort	
 
Age ≥18 years
 
Arrival to an intervention or control ED during study period
 
First recorded temperature ≥38.0°C
 
First-recorded vital sign data meets ≥2 of:         
 
a. Systolic blood pressure <90 mmHg
 
b. Glasgow Coma Scale (GCS) score <15
 
c. Respiratory rate ≥22 breaths/min or oxygen saturation <85%
 
 
 
	
 
Trauma patient
 
Received antibiotics within 6 hours prior to study ED arrival
 
Subsequent eligible ED visit after first eligible encounter during an analysis window
 
Left ED without evaluation or treatment
 
	cohort_risk

Cohort	Inclusion	Exclusion	Cohort eligibility indicator variable*
Sepsis	(1) Age ≥18 years	(1) Trauma patient	cohort_mimics
mimic	(2) Arrival to an intervention or control ED during study period	(2) Received antibiotics	

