### Power

It was estimated that the intervention ED provides care for 1,650 sepsis patients annually (approximately 4.5 sepsis patients per day) and the control EDs together care for a total of 2,200 sepsis patients annually (approximately 6 sepsis patients per day). Estimated control door-to-antibiotic time for ED sepsis patients was an average 170 (±75) minutes based on 2013-2017 data from study hospitals, with approximately 5-10% of patients receiving antibiotics within 1 hour of ED arrival. Based on these assumptions, we estimated 90% power to detect a difference-in-differences change of 16 minutes or more in door-to-antibiotic time associated with Code Sepsis implementation, with the measurement population being all ED sepsis patients. Power calculations employed Monte Carlo simulations.

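### The SAP's false-positive infection rate is calculated only among patients who already met the ED sepsis criteria, so on its own it cannot show that Code Sepsis adds no treatment of uninfected patients

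*SAP*

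**What the plan says.** The SAP (Safety outcomes) defines the false-positive presumptive infection diagnosis rate in the sepsis cohort: "Final adjudicated infection status is" not infected, "among ED patients meeting sepsis" criteria. The variable is `uninfected`. Under Data analysis, safety outcomes are estimated by difference-in-differences (DID), without multiplicity adjustment, and are called hypothesis generating.

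The SAP (Inclusion/exclusion criteria) admits a patient to the sepsis cohort only if all three of these hold:

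- organ failure: "Acute organ failure in the ED defined by SOFA score while in the ED", at least 2 points above baseline;
- treatment: at least one dose of IV or "IV-equivalent antibiotics while in the ED for suspected infection (i.e. antibiotics not given for prophylaxis");
- culture: at least one of the "body fluid cultures while in the ED".

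The Protocol (section 3.2) hypothesizes that team activation "decreases door-to-antibiotic time without increasing overtreatment".

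**The concern.** A patient enters the denominator only after being treated and cultured in the ED and scored as having organ dysfunction. The Code Sepsis steps in Protocol section 5.2 act on these conditions: early blood and urine sampling, point-of-care tests, a timed decision huddle and antibiotics brought to the bedside. The intervention can therefore change who is counted. The rate answers how often a patient who met the ED sepsis criteria turns out to be uninfected. The overtreatment hypothesis asks something else: whether more uninfected ED patients are treated than would have been otherwise.

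This is the only planned DID safety outcome that uses adjudicated infection status. If a flat or falling value is read as support for the overtreatment part of the hypothesis, it may give reassurance that it cannot carry.

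**Working it through.** The plan gives no expected value, margin or power for this outcome, so there is no figure to reproduce.

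**Inputs from the documents.** SAP Power: "the intervention ED provides care for 1,650 sepsis patients annually", and 2,200 a year at the two control EDs together. Protocol Table 1: 89,000 annual visits at the intervention ED, and 49,000 + 65,000 = 114,000 at the control EDs.

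**Assumptions.** The uninfected share of the cohort is not given; 12% is used for the example and 10–30% for the range. The 350 added patients are illustrative.

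**1. Behaviour of the rate.** Let U be cohort patients who are uninfected and I those who are infected. The rate is U/(U+I). If U rises by a fraction a and I by a fraction b, it becomes U(1+a)/[U(1+a)+I(1+b)]. It is flat when b = a, falls when b > a and rises when b < a. Equivalently, the direction depends on whether the added patients are uninfected less or more often than the baseline cohort.

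**2. Example.** Baseline U = 0.12 × 1,650 = 198. Add 350 patients, giving 2,000.

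| Uninfected among the 350 | U after | Change in U | Rate (baseline 12.0%) |
|---|---|---|---|
| 8% (28) | 226 | +14% | 226/2,000 = 11.3% |
| 12% (42) | 240 | +21% | 240/2,000 = 12.0% |
| 20% (70) | 268 | +35% | 268/2,000 = 13.4% |

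Per 1,000 visits, the 8% row goes from 198/89 = 2.22 to 226/89 = 2.54. A population denominator shows the rise while the planned rate falls.

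**3. Range of baselines.** Raise U by 20% at baseline shares of 10/20/30% (U = 165/330/495, so +33/+66/+99 patients a year).

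- If I also rises 20%, the rate stays at 10.0/20.0/30.0%.
- If I rises 30%, it falls to 9.30/18.75/28.35%.
- If I does not rise, it increases to 11.76/23.08/33.96%.

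**4. Patients outside the cohort.** Extra uninfected patients treated without a culture or without the SOFA rise do not change the rate at all. One hundred of them would move all-ED antibiotic use by 100/89,000 = 0.11 percentage points.

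**5. Precision of a population-denominator outcome.** Take the 8% row, with controls stable at 0.12 × 2,200 = 264 events in each period, simple Poisson counts and two-sided 5%.

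- Ratio scale: ln(226/198) = 0.132; SE = √(1/198 + 1/226 + 2/264) = 0.131; z = 1.01; power about 17%. If that rise were observed, the 95% interval would run from about −12% to +47%.
- Difference scale, per 1,000 visits: 28/89 = 0.315; SE = √[(198+226)/89² + 2×264/114²] = 0.307; power about 18%.

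For the same 14% rise, the ratio-scale calculation gives about 15%, 26% and 36% power at baseline shares of 10%, 20% and 30%.

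**The case against.** **Overtreatment already has its own outcome.** The SAP measures ED antibiotics in sepsis mimics, a denominator not conditioned on treatment. It also plans 24-hour antibiotic use in all ED patients and in the high-risk cohort, and the PPV of activation for infection. This stands in part: the plan is not blind to overtreatment. But the mimic cohort covers only heart failure and venous thromboembolism, utilization ignores infection status, and the PPV for infection is confined to activations at the intervention ED in the post period, with no pre-period or control comparison.

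**Masking is only one possibility.** This stands. On the 12% base, a falling rate needs more than 88% of added patients to be infected. The SOFA requirement also limits how mild the added patients can be. A reader might infer that the rate will conceal added overtreatment; the documents do not support that, because they give neither the baseline share nor the mix of added patients, and at 20% uninfected the rate rises.

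**Growth in the cohort would be visible.** Going from 1,650 to 2,000 against a stable 2,200 at the control EDs gives ln(2,000/1,650) = 0.192, SE = √(1/1,650 + 1/2,000 + 2/2,200) = 0.045 and z of about 4.3. Rate times cohort size then recovers the count of treated uninfected patients. This is correct and useful, but cohort size is not a listed outcome, so nothing commits the analysis to that step.

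**A population denominator has its own bias.** Its numerator still requires an ED antibiotic, a culture and a SOFA rise. If antibiotics or cultures move from the ward to the ED, it can rise with no extra patient treated. This stands, and it is why the new outcome should sit beside the existing one and not replace it.

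**Conclusion.** The point holds as a limit on interpretation with an inexpensive remedy. The planned rate is 1 − PPV of meeting the ED sepsis criteria. It can stay flat or fall while more uninfected patients are treated, provided the added patients are no more often uninfected than the baseline cohort. In the worked cases, rises of 14% and 21% in treated uninfected patients go with rates of 11.3% and 12.0% against a 12.0% baseline. That condition is arithmetic and does not depend on the assumptions. The sizes do depend on the assumed 12%, 8% and 350.

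The per-1,000 figures are illustrative, because the 89,000 visits are not restricted to eligible adult non-trauma patients. The 1,650 is the plan's own conservative figure; the 2.8% in Protocol section 4.1 would give 0.028 × 89,000 = 2,492.

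The primary analysis is unaffected, and the safety outcomes are already labelled hypothesis generating. A change is worth making because no other DID outcome based on adjudicated infection status would show an increase in treated uninfected patients.

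**What to change.** 1. Keep the planned share, label it 1 − PPV of meeting the ED sepsis criteria, and state that it will not be read alone as evidence of no added overtreatment.
2. Add a DID safety outcome: met the ED sepsis criteria and adjudicated uninfected, with all eligible adult non-trauma ED patients or encounters as denominator.
3. Apply one set of exclusions to numerator and denominator. As written, `cohort_sepsis` lacks two exclusions that `cohort_all` has: antibiotics in the 6 hours before arrival, and leaving without evaluation or treatment.
4. Use the all-encounter (`_sens`) set only if repeat encounters are adjudicated, which the documents do not say. Otherwise count one qualifying encounter per patient per analysis window.
5. Report sepsis-cohort size by site and phase, and read the new outcome beside 24-hour antibiotic use in all ED patients, so that a shift from ward to ED is not mistaken for added treatment.

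The cost is one recoded outcome built on the existing `uninfected` variable, plus a table of cohort sizes. The drawback is imprecision: with about 17–18% power for a 14% rise at an assumed 12% baseline, report the estimate with its interval, and do not treat a non-significant result as showing no increase.
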